10.6 Time to Death

From date of registration to date of death due to any cause. Patients last known to be alive are censored at date of last contact.

### 10.7 Duration of Response (DoR)

From date of first documentation of response (CR or PR) to date of first documentation of progression or symptomatic deterioration (as defined above), or death due to any cause among patients, who achieve a response (CR or PR). Patients last known to be alive without report of progression are censored at date of last contact.

## 11.0 STATISTICAL CONSIDERATIONS

### 11.1 Sample Size and Accrual Goals

The primary objective of the study is to compare overall survival (OS) between the 2 treatment arms. We estimate the median OS of patients treated with FOLFIRI to be 6 months in this population. (113,114) Assuming that the addition of ABT-888 offers an increase in OS to 9 months (HR 1.5), we will need 128 eligible patients, based on a 1:1 randomization, a one-sided type 1 error of 10% and 80% power. Allowing for an approximately 10% ineligibility rate, accrual will be to a total of 143 patients. We expect 28 months of accrual and 10 months of follow-up. Our accrual rate estimate is based on the observed accrual to SWOG study **S1115**.

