### 11.2 Analysis of Primary Endpoint

The primary analysis of OS will be conducted in all eligible patients according to the intent-to-treat principle, using the log-rank test with stratification by prior systemic treatment for metastatic disease. Distributions of overall survival in Arms 1 and 2 will be estimated using the method of Kaplan-Meier. The final analysis will take place upon the observation of approximately 110 deaths.

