### 11.3 Interim Analysis

An interim futility analysis of progression-free survival (PFS) by treatment arm will be performed by testing an alternative hypothesis of a 1.5 HR at  $p < 0.05$  when approximately 35% of the expected PFS events in the control arm have been observed. We expect this analysis to occur when approximately 50% of the study sample has been accrued. Unless there are toxicity concerns or extenuating circumstances, the study will not close during this interim assessment. If this alternative hypothesis is rejected at  $p < 0.05$  then the study may be closed to further accrual and the experimental agent declared of no interest for further development. If we fail to reject this hypothesis, the study will complete accrual.

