### 11.5 Translational Endpoints

We assume that 90% of eligible patients will submit tissue and 80% of these will be successfully assayed. With 128 eligible patients enrolled on S1513, it is estimated that for each arm, 46 patients (n=92 total) will be included in analyses. The overall prevalence of each biomarker can be estimated to within 10% (95% confidence interval).

- a. The primary translational objective is to evaluate if *BRCA1* and *BRCA2* mutations (somatic or germline) are associated with improved clinical outcomes (OS, PFS, and ORR) in each treatment arm. Prevalences of *BRCA1* and *BRCA2* mutations in this patient population are estimated to be approximately 1-2% and 5-7%, respectively.
- b. Secondly, we will evaluate the impact of HRD positivity on clinical outcomes in each treatment arm. Although the HRD score threshold for positivity has yet to be determined in this disease, we will first dichotomize the score at its observed median value (represented as 50% prevalence in the tables below), and estimate the associations between that binary predictor and clinical outcomes. We will also assess the associations of HRD score as a continuous variable with clinical outcomes.
- c. Additionally, we will evaluate the impact of other exploratory genomic alterations (other than *BRCA1/2* mutations) identified by the BROCA-HR assay on clinical outcomes in each treatment arm.

We will evaluate if each potential biomarker is associated with the clinical outcomes of overall survival (OS), progression-free survival (PFS), and response rate (ORR) separately by treatment arm. The associations between each potential biomarker and both OS and PFS will be explored via Kaplan-Meier curves and Cox regression. We assume the baseline median OS is 6 months, 46 patients enrolled over 28 months and an additional 10 months of follow-up. The following table shows approximate power to detect OS hazard ratios of 2.5, 3, and 3.5, corresponding to median OS of 15, 18, and 21 months in the biomarker-positive subgroup, using a two-sided alpha of 0.1, for a range of biomarker frequencies.

| Biomarker Prevalence | Power  |        |          |
|----------------------|--------|--------|----------|
|                      | HR=2.5 | HR = 3 | HR = 3.5 |
| 5%                   | 30%    | 35%    | 39%      |
| 10%                  | 45%    | 54%    | 60%      |
| 25%                  | 73%    | 83%    | 89%      |
| 50%                  | 86%    | 93%    | 97%      |

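### Is the 80% power in Section 11.1 too high because it leaves out the PFS futility look in Section 11.3?

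*Combined protocol and SAP*

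**What the plan says.** Section 11.1 sizes the trial on overall survival, with medians of 6 and 9 months (hazard ratio 1.5, control over experimental): "we will need 128 eligible patients, based on a 1:1 randomization, a one-sided type 1 error of 10% and 80% power". Section 11.2 fixes the analysis time: "The final analysis will take place upon the observation of approximately 110 deaths".

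Section 11.3 adds one look on a different endpoint: "An interim futility analysis of progression-free survival (PFS) by treatment arm will be performed by testing an alternative hypothesis of a 1.5 HR". The level is p < 0.05, and the timing is tied to events in one arm: "when approximately 35% of the expected PFS events in the control arm have been observed". This is expected at about half of accrual. Three statements govern what follows:

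- "Unless there are toxicity concerns or extenuating circumstances, the study will not close during this interim assessment".
- If the hazard ratio of 1.5 is rejected, "then the study may be closed to further accrual and the experimental agent declared of no interest for further development".
- In the opposite case: "If we fail to reject this hypothesis, the study will complete accrual".

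Section 11.6 gives decisions on termination to the Data and Safety Monitoring Committee. Section 11.3 does not give the side of its p-value. Elsewhere in Section 11 both conventions appear: one-sided for the OS comparison in 11.1, and, for the biomarker power tables in 11.5, "using a two-sided alpha of 0.1, for a range of biomarker frequencies".

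**The concern.** A futility rule can stop a trial that would have ended positive, so it costs power. A reader may take the 80% in 11.1 as the power of the whole design, yet nothing there sets power aside for the look and no section gives the two together. If the look costs power, the chance of missing a real gain from 6 to 9 months is above the implied 20%.

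The unstated side adds to this. It determines how poor the interim PFS result must be before a hazard ratio of 1.5 counts as rejected. Because 11.1 and 11.5 use different conventions, the side seems at first impossible to infer. The sentence saying that the study will not close during the assessment also stands just before one saying that it may be closed.

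**Working it through.** **The plan's own figure.** Inputs from 11.1: hazard ratio 1.5, one-sided 0.10, power 80%, 1:1 allocation.

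- Deaths needed = 4(1.2816 + 0.8416)² / (ln 1.5)² = 109.7, so 110, as in 11.2.
- Power at 110 deaths = Φ(½√110 × 0.4055 − 1.2816) = Φ(0.845) = 80.1%.
- Exponential medians of 6 and 9 months, 64 patients per arm, 28 months of uniform accrual and 10 of follow-up give 109.9 expected deaths.

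The 80% is therefore the fixed-design value. That it excludes the look is inferred from this match, because 11.1 does not say so.

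**When the look falls.** If all 64 control patients eventually have a PFS event, 35% is 22.4 events. With the 3-month median PFS used in 11.5, that number is reached at month 13.96, which is 49.8% of the 28 months and agrees with the half stated in 11.3. At a PFS hazard ratio of 1.5 (median 4.5 months) Arm 1 then has 18.8 events, for a total of 41.2.

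**What the side changes.** The look rejects when the estimated log hazard ratio (control over experimental) is below ln 1.5 − z × 2/√41.2, with 2/√41.2 = 0.3116.

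| Futility tail | z | Boundary, log scale | Rejects if Arm 1/Arm 2 PFS hazard ratio exceeds |
|---|---|---|---|
| 0.05 | 1.645 | −0.107 | about 1.11 |
| 0.025 | 1.960 | −0.205 | about 1.23 |

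Under either tail the experimental arm must look worse than control on PFS before the rule is met.

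**Power if the look is always followed.** Assume a true PFS hazard ratio of 1.5 and let ρ be the correlation between the interim PFS and final OS test statistics. The protocol gives no value for ρ. If the two endpoints carried the same information, ρ would be √(41.2/110) = 0.61. The bivariate normal probability that the final Z exceeds 1.2816 and the look does not reject is:

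| ρ | 0.05 tail | 0.025 tail |
|---|---|---|
| 0 | 76.1% | 78.1% |
| 0.2 | 76.7% | 78.5% |
| 0.4 | 77.5% | 78.9% |
| 0.6 | 78.5% | 79.5% |

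The loss from 80.1% for ρ of 0.2–0.6 is 1.6–3.4 points with the 0.05 tail and 0.6–1.6 with the 0.025 tail. At ρ = 0 it is 4.0 and 2.0 points. If the look were acted on half the time, power would be 78.4–79.3% or 79.3–79.8%.

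**Simulation checks.**

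- 30,000 trials per scenario, log-rank test at the 110th death: 79.6–79.7% without the look. With the look followed, 76.9% and 78.1% (0.05 tail) and 78.3% and 79.0% (0.025 tail), at observed correlations of 0.30 and 0.60.
- 6,000 trials per scenario, with other dependence structures: 75.3–77.9% and 77.5–79.3%, against fixed-design values of 79–81% in the same runs. The lowest values belong to independent endpoints.
- No effect on either endpoint: rejection of the OS null is 10.1% without the look, 8.3% (0.05 tail) or 8.9% (0.025 tail) if it is followed. The look stops about 37% or 27% of such trials.

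**Scale.** Section 11.2 asks for approximately 110 deaths. By the same formula 105 deaths give 78.7% and 100 give 77.2%.

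**The case for a change.** The best case for a change is the side of the test. An observed Arm 1/Arm 2 PFS hazard ratio of 1.15 would meet the rule under one reading and not under the other, and with no PFS effect the look would stop 37% or 27% of trials. Anyone describing the look needs to know which applies. It can also be said that an advisory rule is a reason to state how power depends on it. And the loss grows if the PFS effect is weaker than the OS effect: at a PFS hazard ratio of 1.3 (an assumption, not in the protocol), with the look always followed, power is 71.8–75.0% (0.05 tail) or 75.5–77.7% (0.025 tail).

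Part of this stands: the tail is not written down, and a report of the look should give the one used. The ambiguity is narrower than it seems, though. Rejection leads to the agent being dropped, so only a result pointing to less benefit can count, and the open choice is a 0.05 or a 0.025 tail. The comparison between arms in 11.1 is one-sided. The two-sided level in 11.5 is for biomarker associations within each arm and says little about this test. A 0.05 tail is the natural reading.

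The weaker-PFS case is the trade-off of any futility look on an earlier endpoint. It chiefly affects trials in which PFS shows little, and the Committee remains free to continue. A power sentence added to 11.1 would have to rest on a correlation found nowhere in the protocol, and would change with the value chosen.

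**Conclusion.** No change follows. The 80% is arithmetically right for the design in 11.1 and remains right if the non-binding look is not acted on. If it were always followed at a PFS hazard ratio of 1.5, the cost would be roughly 0.5 to 3.5 points, depending on the tail and on an assumed correlation of 0.2–0.6 between the two test statistics. That is similar to the slack in the plan's approximate death count. Patients, deaths, alpha and the primary test would all stay as they are, and type I error falls slightly if the look is followed.

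The unstated tail is a gap that analysts can fill sensibly. The sentence about not closing during the assessment most naturally means that accrual continues while the analysis is run, so it does not conflict with possible closure afterwards. The Revision #1 memorandum records that accrual is permanently closed and all patients are off treatment, so restating prospective power could no longer affect an accrual decision. The protocol does not say whether the look took place.

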### 11.2 Analysis of Primary Endpoint

The primary analysis of OS will be conducted in all eligible patients according to the intent-to-treat principle, using the log-rank test with stratification by prior systemic treatment for metastatic disease. Distributions of overall survival in Arms 1 and 2 will be estimated using the method of Kaplan-Meier. The final analysis will take place upon the observation of approximately 110 deaths.

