#### 5.3 Clinical/Laboratory Criteria

- a. Patients must have a Zubrod Performance Status of 0-1 (see [Section 10.4](#)).
- b. Patients must be  $\geq 18$  years of age.
- c. Patients must have adequate hematologic function as evidenced by all of the following within 14 days prior to registration: ANC  $\geq 1,500/\text{mcL}$ ; hemoglobin  $\geq 9$  g/dL; and platelets  $\geq 100,000/\text{mcL}$ .

- d. Patients must have adequate hepatic function as evidenced by all of the following within 14 days prior to registration: total bilirubin  $\leq 1.5 \times$  Institutional Upper Limit of Normal (IULN); serum albumin  $\geq 3.0$  g/dL; and AST and ALT  $\leq 2.5 \times$  IULN. Patients with liver metastases may have AST and ALT of  $\leq 5.0 \times$  IULN.
- e. Patients must have adequate renal function as evidenced by the following within 14 days prior to registration: serum creatinine  $\leq 2.0$  mg/dL.
- f. Patients must have CA19-9 obtained within 14 days prior to registration. If CA19-9 is normal, then CEA must be tested within 14 days prior to registration.
- g. Patients must have BUN, alkaline phosphatase, sodium, potassium, calcium, glucose, chloride, and carbon dioxide levels obtained within 14 days prior to registration.
- h. Patients must not have any clinically significant and uncontrolled major medical condition(s) including, but not limited to uncontrolled nausea/vomiting/diarrhea; active uncontrolled infection; symptomatic congestive heart failure (NYHA Class  $\geq$  II) (see [Section 18.2](#)); unstable angina pectoris or cardiac arrhythmia; psychiatric illness/social situation that would limit compliance with study requirements.
- i. Patients must not have active seizure or history of seizure.
- j. Patients must be able to swallow whole capsule.
- k. Patients must have a complete physical examination and medical history within 28 days prior to registration.
- l. Patients must not have known Gilbert's Syndrome.
- m. Patients must not have known hypersensitivity to irinotecan, fluorouracil, or leucovorin.

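### The primary OS test is valid and correctly powered, but it leaves out Zubrod status and CA19-9, which every eligible patient has at baseline; if they are prognostic, adjusting for them would add power.

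*Combined protocol and SAP*

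**What the plan says.** Section 11.2 analyses all eligible patients by intention to treat, "using the log-rank test with stratification by prior systemic treatment for metastatic disease", at approximately 110 deaths. Section 6.0 names the same factor, and no other, for the dynamic balancing at randomisation.

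Section 5.3 sets two baseline requirements that matter here: "Patients must have a Zubrod Performance Status of 0-1" and "Patients must have CA19-9 obtained within 14 days prior to registration". Section 5.0 asks sites to enter the results of tests required for eligibility on the Onstudy Form, so both values should be essentially complete in the analysis set. If CA19-9 is normal, Section 5.3 also requires a CEA.

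Section 11.1 gives the design: "We estimate the median OS of patients treated with FOLFIRI to be 6 months in this population", an improvement to 9 months (hazard ratio 1.5), and "a one-sided type 1 error of 10% and 80% power". It continues: "we will need 128 eligible patients, based on a 1:1 randomization".

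Section 11 names no covariate-adjusted comparison of the arms. Cox regression appears only in Section 11.5, for biomarker associations within each arm. No section says how strongly Zubrod status or CA19-9 predicts survival.

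The Revision #1 memorandum states that accrual is permanently closed and that no patient remains on treatment.

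**The concern.** When a baseline variable predicts survival, a log-rank test that ignores it is usually less powerful than a test that uses it. The plan collects two such candidates from everyone, yet neither is balanced at randomisation nor used in the analysis.

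The one factor that is used may explain little. Section 5.2 requires one prior regimen for metastatic disease unless the exception in 5.2c applies, so the stratum without such treatment consists of exceptions. Its size is not stated, but it is probably small.

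Two things are at stake: power that might be had from data already collected, and a pre-specified way to handle a chance imbalance in either variable.

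**Working it through.** **Inputs.** From Sections 11.1 and 11.2: one-sided alpha 0.10, 80% power, hazard ratio 1.5 (control over experimental), medians 6 and 9 months, 128 eligible patients at 1:1, 28 months of accrual plus 10 of follow-up, about 110 deaths, 143 accrued with 10% ineligible. Assumed, because the documents are silent: the prognostic hazard ratios in the table; half of patients Zubrod 1; log CA19-9 normally distributed with a linear effect; 90% with prior systemic treatment for metastatic disease, and that factor not prognostic.

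**Step 1: the plan's own figures.**
- Deaths (Schoenfeld): 4(1.2816 + 0.8416)² / (ln 1.5)² = 4 × 4.508 / 0.1644 = 109.7, so 110.
- Power at 110 deaths: Φ(√110 × ln 1.5 / 2 − 1.2816) = Φ(0.845) = 80.1%.
- Probability of death, exponential survival with uniform accrual: 1 − [exp(−10λ) − exp(−38λ)] / (28λ), with λ = ln 2 / median. This gives 0.906 (control) and 0.810 (experimental), mean 0.858. Then 128 × 0.858 = 109.9 deaths.
- Accrual: 128 / 0.90 = 142.2, so 143.

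All of the stated figures reproduce.

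**Step 2: planned test against adjusted test.** Each cell has 4,000 simulated trials, with 64 patients per arm, analysis at the 110th death and one-sided 10%. The planned stratified log-rank test and a stratified Cox model adding Zubrod status and log CA19-9 were run on the same trials. Control median survival was set to 6 months.
- Reading A: 1.5 is the hazard ratio given the covariates. The medians are then 6 and 9 months.
- Reading B: the arm-level (unadjusted) hazard ratio is calibrated to about 1.5.

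| Zubrod HR / CA19-9 HR per SD | Arm-level HR under A | A: log-rank → adjusted | B: log-rank → adjusted |
|---|---|---|---|
| 1.0 / 1.0 | 1.503 | 79.1 → 78.8% | 79.2 → 78.8% |
| 1.2 / 1.2 | 1.488 | 77.6 → 78.7% | 78.2 → 79.4% |
| 1.3 / 1.3 | 1.479 | 75.5 → 78.8% | 78.2 → 80.4% |
| 1.5 / 1.3 | 1.469 | 74.0 → 77.4% | 77.5 → 81.5% |
| 1.5 / 1.5 | 1.440 | 71.6 → 78.3% | 78.8 → 85.1% |
| 2.0 / 1.5 | 1.426 | 68.5 → 78.1% | 77.7 → 85.6% |

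Simulation error is about 0.7 points per cell. Under the null, both tests rejected in 9.5% to 10.3% of trials.

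Gains, as differences of the rounded figures:
- A: −0.3, +1.1, +3.3, +3.4, +6.7, +9.6 points.
- B: −0.4, +1.2, +2.2, +4.0, +6.3, +7.9 points.

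**Step 3: the gain in deaths.** Deaths needed scale with (1.2816 + z for power)². Under A at 2.0/1.5, 110 × [(1.2816 + 0.775)² / (1.2816 + 0.482)² − 1] is about 40 extra deaths for the log-rank test to match. The same sum gives about 12 at 1.3/1.3 and 4 at 1.2/1.2.

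**Step 4: chance imbalance.** With 64 per arm and half Zubrod 1, the between-arm difference in Zubrod 1 patients has SD √(2 × 64 × 0.25) = √32 = 5.66. A difference of 7 or more (7/64, about 11 percentage points) has probability about 2[1 − Φ(6.5/5.66)] = 2[1 − Φ(1.15)], or 25%.

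**Step 5: the 50/50 assumption.** An even split favours Zubrod status as a covariate. In a separate run of 3,000 trials per cell at 2.0/1.3, the gain fell from 6.4 points at 50/50 to 4.3 with Zubrod 1 in either 20% or 80% of patients.

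**The case against.** The strongest reply is that nothing here is wrong. The test stratifies by exactly the factor used at randomisation, it holds its type I error, and its power reproduces. Choosing a stratified log-rank test over an adjusted Cox model is defensible. All of that stands: this is a missed efficiency, not an error.

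A reader might infer that the trial loses power against its stated 80%, or that its hazard ratio is biased towards 1. The documents support neither. Section 11.1 expresses the effect at arm level, with no covariates, as medians of 6 and 9 months and a hazard ratio of 1.5. These agree exactly only if survival within each arm is exponential. If 1.5 is the arm-level hazard ratio, the planned test keeps 77.5% to 79.2% simulated power, and adjustment is an extra rather than a repair. A shortfall appears only under reading A, and only with prognostic strengths that the documents do not give. The smaller arm-level hazard ratio under A reflects a different estimand, not a fault in the planned analysis.

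It is also fair that the largest gains need a Zubrod hazard ratio of 2.0 in a trial limited to levels 0 and 1, and a correctly specified CA19-9 effect. The upper end of the range should not be taken as the expected case.

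On imbalance, the planned test is already valid averaged over randomisations. What adjustment adds is a correction in the particular trial that was run. Finally, because accrual is closed, replacing a primary test is credible only under a timing condition. That objection shapes the remedy but does not remove the point.

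**Conclusion.** The point holds as a conditional gain in efficiency. At the planned 128 patients and 110 deaths, adjusting for Zubrod status and log CA19-9 changes power by about 0 points if neither is prognostic, +1 if weak, +2 to +4 if modest and +6 to +10 if strong. The direction is the same whether 1.5 is read as a conditional or an arm-level hazard ratio; the range is about 0 to 10 points under the first and 0 to 8 under the second.

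These figures depend on assumed prognostic strengths, an even Zubrod split and a log-linear CA19-9 effect, none of which the documents supply. The case for change rests on asymmetry: the possible loss is within about 1 point, the possible gain is several, and no further data are needed. It does not show that the trial is underpowered or that its primary test is invalid.

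**What to change.** Amend Section 11.2 before any comparative OS data are seen:
- **Primary test:** the one-sided 10% test of the treatment term in a Cox model stratified by prior systemic treatment for metastatic disease, with Zubrod 0 vs 1 and log baseline CA19-9 as covariates.
- **CA19-9 rule:** enter normal values at their measured level, and values below the detection limit at a pre-stated value such as that limit. The CEA taken in patients with normal CA19-9 does not replace the baseline CA19-9 value.
- **Supportive:** keep the stratified log-rank test and the Kaplan-Meier curves.

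If comparative OS data have already been seen, leave the stratified log-rank test as primary and report the adjusted model as a labelled sensitivity analysis.

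The cost is wording in the statistical section, with no extra patients, deaths or data collection. The reported hazard ratio becomes conditional on the covariates, and up to about 1 point of power is lost if neither variable is prognostic.
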